Appendix 2. Algorithm for Calculating Disease Flare

Disease Flare is a worsening of $\geq 30\%$ from baseline in at least 3 of the 6 juvenile idiopathic arthritis (JIA) American College of Rheumatology (ACR) core set criteria and an improvement of $\geq 30\%$ in no more than 1 of the criteria.

- active joint count,
- limited range of motion joint count,
- physician global assessment of disease activity,
- parent's global assessment of well-being,
- physical function as measured by Childhood Health Assessment Questionnaire (CHAQ), and
- erythrocyte sedimentation rate (ESR).

% change from baseline at a visit is calculated as:

$$(\text{value at visit} - \text{baseline value}) * 100 / \text{baseline value}$$

Change at a visit is calculated as:

$$\text{value at visit} - \text{baseline value}$$

The following abbreviations will be used throughout this appendix to refer to the items needed in the algorithm definitions:

Parameter	Abbreviation for the Parameter
% change from baseline in active joint count	AJ73
% change from baseline in limited range of motion joint count	LOM69
% change from baseline in parent's global assessment of well-being	PGAWB
% change from baseline in physician's global assessment of disease activity	PHYGA
% change from baseline in physical function as measured by Childhood Health Assessment Questionnaire (CHAQ)	CHAQ
% change from baseline in erythrocyte sedimentation rate (ESR)	ESR
Change in active joint count	aj73
Change in limited range of motion joint count	lom69
Change in parent's global assessment of well-being	pgawb
Change in physician's global assessment of disease activity	phyga
Value of erythrocyte sedimentation rate	esr

Note:

- An *esr* value is within normal range if it is at most 20.
- If the *esr* is elevated (*esr* >20) due to JIA, then *esr* is used for calculation.
- If the *esr* is elevated due to a reason other than JIA, then *esr* is not used for calculation.
- If both baseline and postbaseline value of *esr* is within normal range (≤ 20), then the percent change of *esr* is set at 0 (no change).
- If either the number of joints with active arthritis or the number of joints with limitation of motion are used in the calculation of flare for a study visit, then a minimum worsening of at least 2 active joints or 2 joints with limitation of motion must be present.
- If either the Physician's Global Assessment of Disease Activity or the Parent's Global Assessment of Well-Being are used in the calculation of flare for a study visit, then a minimum worsening of at least 20 mm in 0 to 100 mm visual analogue scale (VAS) or 2 scores in the VAS of 21 circles from 0 to 10 must be present.

Flare Calculation

Calculation of flare (two-step calculation; the first step calculates improvement, and the second step calculates worsening).

Step 1: Improvement:

Check $\geq 30\%$ improvement. Specifically, check if percent change from baseline is less than or equal to -30% , i.e.,

$$\text{if } (\text{parameter} \leq -30\%) = 1, \text{else } 0$$

Count how many variables have not less than 30% improvement, if the improvement count is 2 or more, conclude that the patient is a non-flare patient. If the improvement count is 1 or less, proceed to Step 2.

Step 2: Worsening

Check $>30\%$ worsening. Specifically check if percent change from baseline is more than 30% , i.e.,

$$\text{Criteria 1: if } (\text{parameter} \geq 30\%) = 1, \text{else } 0$$

For variable: active joint count, limit of motion joint count, and Physician's Global Assessment of Disease Activity, also evaluate

$$\text{Criteria 2: if } (\text{variable at visit} - \text{variable at randomization} \geq 2) = 1, \text{else } 0$$

Note: if any of active joint count, limit of motion joint count, or physician assessment of disease activity has baseline value = 0, only Criteria 2 is required to determine the worsening, otherwise both Criteria 1 and 2 are required.

For variable: Parent's Global Assessment of Well-Being, also evaluate

*Criteria 3: if (variable at visit – variable at randomization $\geq 20\text{mm}$)
= 1, else 0*

Note: if Parent's Assessment of Patient Well-Being is with baseline value = 0, only Criteria 3 is required to determine the worsening, otherwise both Criteria 1 and 3 are required.

If baseline value of ESR is 0 and post-baseline value is nonmissing and out of normal range (i.e. ESR $>20\text{ mm/hr}$), consider it as worsening.

Count how many variables are worsening. If the worsening count is 3 or more, conclude as a flare patient, otherwise conclude as a non-flare patient.

Note:

Scenario 1: If no variable is missing, proceed as described in Step 1 and/or Step 2 whichever applies.

Scenario 2: If there are variables missing at postbaseline, apply LOCF first at component level, then back to Scenario 1 (LOCF cannot be applied across study periods and the patient needs to have at least 1 postbaseline visit to apply LOCF. The baseline value cannot be carried forward).

Note for ESR: If the *esr* at a particular visit is missing, then the last observation is carried forward for the visit. However, for the LOCF visit, if the elevation is attributable to a medical condition other than the study condition as well, then the *esr* value at the current visit is treated as missing.

Scenario 3: If there are variables missing at baseline, use nonmissing components as the core sets and back to Scenario 1. Unless otherwise specified, if there are variables with baseline value = 0, all postbaseline percent improvement is not calculatable, hence consider these variables as missing and use nonmissing components as core sets and back to Scenario 1.

Note: for Scenario 3:

- If 1 component is missing, the rest of 5 components will be used as core set. If 3 out of 5 components are worsening and no more than 1 out of 5 is improving, the patient will be considered as a flare patient.
- If 2 components are missing, the rest of 4 components will be used as core set. If 3 out of 4 components are worsening and no more than 1 out of 4 is improving, the patient will be considered as a flare patient.
- If 3 components are missing, the rest of 3 components will be used as core set. If all 3 components are worsening, the patient will be considered as a flare patient.
- If more than 3 components are missing, there will not be sufficient information, thus the patient will be considered as a non-flare patient.

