
Primary
 
 To evaluate the efficacy of ixekizumab in children with JIA subtypes of ERA (including JoAS) and JPsA based on the JIA American College of Rheumatology (ACR) 30 response 	Percentage of participants meeting the JIA ACR 30 response criteria at Week 16

Secondary for the Open Label Treatment (OLT) and Open Label Extension (OLE) Periods
 
 To evaluate the efficacy of ixekizumab in children with JIA subtypes of ERA (including JoAS) and JPsA based on the other clinical responses, disease activity and physical function measures To evaluate the efficacy of adalimumab (reference arm) in children with JIA subtypes of ERA (including JoAS) and JPsA based on JIA ACR 30 and the other clinical responses, disease activity and physical function measures To characterize ixekizumab pharmacokinetics (PK) in children with JIA subtypes of ERA (including JoAS) and JPsA 	
The following outcomes will be assessed at each regular study visita:
 
 Percentage of participants meeting the JIA ACR 30/50/70/90/100 response criteria Changes from baseline in each of the 6 individual components of the JIA ACR core set variables as follows: 
 Number of active joints Number of joints with limited range of motion Physician's Global Assessment of Disease Activity Parent's Global Assessment of Well-Being Physical function as measured by the Childhood Health Assessment Questionnaire (CHAQ) Acute-phase reactant (high-sensitivity C-reactive protein [hsCRP]) and erythrocyte sedimentation rate (ESR) Change from baseline in Psoriasis Area and Severity Index (PASI) for JPsA participants with at least 3% Body Surface Area (BSA) at baseline Change from baseline in Leeds Enthesitis Index (LEI) for participants with enthesitis at baseline Proportion of participants with disease flare (flare defined as worsening of $\geq 30\%$ from baseline in at least 3 of the 6 JIA ACR core set criteria and an improvement of $\geq 30\%$ in no more than 1 of the criteria) Trough concentrations of ixekizumab in participants with JIA subtypes of ERA (including JoAS) and JPsA

Objectives and Endpoints

Objectives	Endpoints

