9.1.2. Secondary Efficacy Assessments

The secondary efficacy outcomes assessed at each regular visit for all participants are as follows:

- percentage of participants meeting JIA ACR 30/50/70/90/100 response criteria,
- changes from baseline in each of the 6 individual components of the JIA ACR core set variables, and
- proportion of participants with disease flare (flare defined as worsening of $\geq 30\%$ from baseline in at least 3 of the 6 JIA ACR core criteria for JIA and an improvement of $\geq 30\%$ in no more than 1 of the criteria).

In addition, for JPsA participants with plaque psoriasis (at least 3% BSA at baseline), the following secondary efficacy endpoint will be assessed at each regular visit:

- change from baseline in PASI.

In addition, for participants with enthesitis at baseline, the following secondary efficacy endpoint will be assessed at each regular visit:

- change from baseline in Leeds Enthesitis Index (LEI).

9.1.2.1. JIA ACR 50, 70, 90, and 100

JIA ACR 50, JIA ACR 70, JIA ACR 90, and JIA ACR 100 responses are secondary efficacy endpoints and are improvements of at least 50%, at least 70%, at least 90% and at least 100%, respectively, in the JIA ACR criteria set. The JIA ACR 50, JIA ACR 70, JIA ACR 90 and JIA ACR 100 are calculated similarly to JIA ACR 30, as described in Section 9.1.1.1.

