6.1.2.2.1. OLE Period Population

Baseline for OLE Period Population will be defined as the last available value on or before the first injection of study treatment in the OLT Period at Week 0 (Visit 2) for efficacy, health outcomes. For patients without a date of first study drug injection at Week 0 (Visit 2), the last nonmissing assessment on or before randomization date will be used.

Unless otherwise specified, for the safety analyses during the OLE period, baseline is defined as the last available value on or before first injection of either ixekizumab or adalimumab in the OLE period. In most cases, this will be the measure recorded at Week 16 (Visit 7). For treatment-emergent adverse events (TEAEs), baseline are adverse events (AEs) which started prior to the study drug injection at Week 16 (Visit 7).

Additional Population Information

For patients who were initially randomized to adalimumab at Week 0 and were switched to ixekizumab by their investigators, only data up to the time of initiation of a switch to ixekizumab will be included in the OLE Period analyses using the OLE Period Population. These patients will be considered nonresponders to categorical assessment per the NRI method after the switch to ixekizumab. Data collected after switch to ixekizumab therapy has started will be summarized separately for the Switcher Population (Section [6.1.2.2.2](#)).

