6.3. Handling of Dropouts or Missing Data

6.3.1. Non-Responder Imputation for Clinical Response

The NRI method may be used to address missingness when the estimand of interest uses the composite strategy for handling intercurrent events.

Analysis of categorical efficacy and health outcome variables will be assessed using a NRI method. Patients will be considered non-responders for the NRI analysis if they do not meet the clinical response criteria or have missing clinical response data at the analysis time point of interest. All nonresponders at Week 16 (Visit 8), as well as all patients who discontinue study treatment at any time prior to Week 16 for any reason, will be defined as non-responders for the

NRI analysis at Week 16. For the OLE Period Population, all non-responders at Week 104 (Visit 29), as well as patients who discontinue the originally assigned study treatment at any time prior to Week 104 for any reason, will be defined as non-responders for the NRI analysis at Week 104. For the Switcher population, all non-responders at Week 104 (Visit 29), as well as patients who discontinue ixekizumab after the switch at any time prior to Week 104 for any reason, will be defined as non-responders for the Week 104 analysis.

The NRI will be applied at any time point specified for analysis.

6.3.2. *Last Observation Carried Forward*

When last observation carried forward (LOCF) is applied, the last nonmissing postbaseline observation on or prior to the missed visit within the same period will be carried forward to subsequent time points for evaluation. Patients without at least 1 postbaseline observation will not be included for evaluation. This method will be used to handle missing data for individual components of a composite endpoint, such as JIA ACR or Disease Flare. Further details are described in [Appendix 1](#) and [Appendix 2](#).

6.3.3. *Modified Baseline Observation Carried Forward*

A complete guideline on statistical principles for clinical trials such as impact on trial design, conduct, and analysis, and documenting estimands and sensitivity analysis can be found in the *ICH E9 Statistical Principles for Clinical Trials* and the *addendum (R1)* (EMA 2020).

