		OLE	Week 16 to Week 104	Summary statistics
				NRI for missing post-baseline values
PASI	OLE Switcher	OLE Switcher	Week 16 (or Switch to IXE) to Week 104	Summary statistics NRI for missing post-baseline values
	PASI total score	ITT – JPsA patients with baseline psoriatic lesion(s) involving BSA $\geq 3\%$	Week 2 to Week 16	Summary statistics
	Change from baseline in PASI total score	OLE – JPsA patients with baseline psoriatic lesion(s) involving BSA $\geq 3\%$	Week 16 to Week 104	mBOCF for missing post-baseline values
	% Improvement in PASI total score			Summary statistics mBOCF for missing post-baseline values
		OLE Switcher – JPsA patients with baseline psoriatic lesion(s) involving BSA $\geq 3\%$	Week 16 (or Switch to IXE) to Week 104	Summary statistics mBOCF for missing post-baseline values
				Summary statistics mBOCF for missing post-baseline values
LEI	Change from baseline in LEI	ITT with baseline LEI > 0	Week 2 to Week 16	Summary statistics mBOCF for missing post-baseline values
		OLE with baseline LEI > 0	Week 16 to Week 104	Summary statistics mBOCF for missing post-baseline values
		OLE Switcher with baseline LEI > 0	Week 16 (or Switch to IXE) to Week 104	Summary statistics mBOCF for missing post-baseline values

Measure	Variable	Population	Analysis Timepoint	Analysis Method
PK	Trough concentrations of ixekizumab in patients with JIA subtypes of ERA (including JoAS) and JPsA	ITT	Week 0 to Week 16	See Section 6.11
Anti-ixekizumab antibodies	Percentage of patients with anti-ixekizumab antibodies	Safety Population	Week 0 to Week 16	See Section 6.12.12
		OLE Population	Week 16 to Week 104	See Section 6.12.12

Abbreviations: ACR = American College of Rheumatology; BSA = Body Surface Area; CHAQ = Childhood Health Assessment Questionnaire; ERA = Enthesitis-related Arthritis; ESR = Erythrocyte Sedimentation Rate; ITT = intent-to-treat; IXE = ixekizumab; JIA = juvenile idiopathic arthritis; JoAS = Juvenile-onset Ankylosing Spondylitis; JPsA = Juvenile Psoriatic Arthritis; LEI = Leeds Enthesitis Index; mBOCF = Modified Baseline Observation Carried Forward; NRI = Nonresponder Imputation; OLE = open-label extension; PASI = Psoriasis Area and Severity Index; PK = Pharmacokinetics; VAS = Visual Analog Scale.

6.9.3. *Other Secondary Efficacy Analyses*

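### Disease flare is an unfavourable event but is imputed by NRI with no stated direction; on the natural reading, imputed participants count as flare-free, most clearly in the adalimumab OLE row

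*SAP*

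**What the plan says.** Protocol Section 9.1.2 lists the "proportion of participants with disease flare" among the secondary efficacy outcomes. SAP Appendix 2 gives the direction: "Disease Flare is a worsening of" at least 30% in three or more of the six core variables, with improvement of that size in no more than one.

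SAP Table RHCG.6.8 assigns flare "NRI for missing post-baseline values" in the ITT, OLE and OLE Switcher rows. Section 6.3.1 explains NRI in terms of response: "Patients will be considered non-responders for the NRI analysis if they do not meet the clinical response criteria or have missing clinical response data". For the OLE it extends the rule to "patients who discontinue the originally assigned study treatment at any time prior to Week 104 for any reason". Section 6.1.2.2.1 says of adalimumab participants who have moved to ixekizumab: "These patients will be considered nonresponders to categorical assessment per the NRI method after the switch to ixekizumab". They remain in the OLE Period Population because Table RHCG.6.1 admits anyone dosed with either drug in the OLE.

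Appendix 2 has its own missing-data rules. Scenario 2 (components missing after baseline) applies LOCF to each component, within a study period only, and requires at least one post-baseline visit. Section 6.3.2 names flare as an endpoint handled this way. Scenario 3 (components missing, or zero, at baseline) works with the remaining components and ends with: "If more than 3 components are missing, there will not be sufficient information, thus the patient will be considered as a non-flare patient".

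**The concern.** NRI is cautious for a favourable outcome because a missing value becomes a failure to meet the criterion. For flare, failing to meet the criterion is the good result. If the same logic is carried over, loss of data or of treatment lowers the reported flare rate, and an arm that retains participants poorly looks steadier than it is.

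The protocol (Section 5.4) gives durability of efficacy as one purpose of the OLE, and flare is one of the endpoints a reader would turn to for that. The OLE is also where adalimumab Week 16 non-responders are switched by rule, so imputation there is built into the design and is not an occasional nuisance.

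**Working it through.** **Which mapping the text favours.** Appendices 1 and 2 are built in parallel. When more than three components are unusable, Appendix 1 classes the participant as a non-responder and Appendix 2 as a non-flare. The SAP's own counterpart of non-responder is therefore non-flare, that is, criterion not met. This is an inference; the SAP does not state it.

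**Whether LOCF rescues the switched participants.** For those switched at Week 16 it does not:
- Section 6.1.2.2 starts the OLE at the first Week 16 injection. The pre-dose Week 16 assessment therefore closes the preceding open-label treatment period, even though Table RHCG.6.8 labels the OLE rows from Week 16.
- Section 6.1.2.2.1 admits only data up to the switch.
- Appendix 2 forbids carrying a value across periods and forbids carrying the baseline value.

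These participants have no on-adalimumab OLE value to carry, so their flare status rests entirely on the undefined NRI mapping. For other discontinuers LOCF could retain a flare, but the SAP does not say whether NRI then overrides it.

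**Size.** The documents state no flare rate, so there is no planned figure to reproduce. Inputs:
- N = 20 adalimumab participants (SAP Section 5.2).
- s = 6 switched. This is assumed from the 71% JIA ACR30 rate at Week 12 that protocol Section 3.2 cites for adalimumab in enthesitis-related arthritis: 29% of 20 is 5.8. Range shown: 4 to 10.
- f = 20% flare among those still assessed. Assumed.
- Dropout on ixekizumab d = 5% to 20%, with f = 10%. Both assumed; protocol Section 8.2 says only that discontinuation should be uncommon.

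Formulas:
- imputed as non-flare: (N − s)f / N = f(1 − s/N)
- assessed only: f
- imputed as flare: ((N − s)f + s) / N

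Adalimumab, OLE Period Population, f = 20%:

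| Switched | Imputed non-flare | Assessed only | Imputed flare |
|---|---|---|---|
| 4 | 3.2/20 = 16% | 20% | 7.2/20 = 36% |
| 6 | 2.8/20 = 14% | 20% | 8.8/20 = 44% |
| 10 | 2.0/20 = 10% | 20% | 12.0/20 = 60% |

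Under the non-flare mapping, the relative reduction equals the share imputed: 20%, 30% and 50%.

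Ixekizumab, f = 10% among those who stay, dropouts imputed as non-flare:
- d = 5%: 0.95 × 10% = 9.5%
- d = 10%: 0.90 × 10% = 9.0%
- d = 20%: 0.80 × 10% = 8.0%

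If dropouts in fact flared at twice the rate (20%), the true proportions would be 10.5%, 11.0% and 12.0%, so the shortfall would be 1 to 4 percentage points.

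**The case against.** The strongest reply is that the SAP never says NRI means non-flare for this endpoint. The opposite mapping would overstate flare, so a downward bias is not proven. That stands. It limits what can be said about direction, but neither mapping yields a sound proportion: one treats every imputed participant as flare-free, the other treats every one as flaring.

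Second, the default sentence in Appendix 2 belongs to Scenario 3 and concerns baseline components. It is not the dropout rule. Missing post-baseline components go through LOCF first, and a participant last seen in flare within the period could be carried forward as a flare. That also stands. A reader might infer that every dropout is flare-free and that all flare rates are certainly too low; the documents do not support either.

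Third, the switch effect is confined to the adalimumab OLE row, where it would flatter the reference arm and not ixekizumab. Flares after the switch are reported in the Switcher Population, and disposition is tabulated by reason (Section 6.5). This stands and limits the consequence.

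Fourth, a reader might take the gap between 14% and 44% as the size of the bias. It is not. Missing ACR30 is not a flare: an unchanged participant is correctly both a non-responder and a non-flare. The gap shows only how far the result depends on an unstated convention.

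Finally, a reader might call the Week 0 anchor for flare an error, because a Week 16 responder who relapses to the pre-treatment level is not a flare. That anchor is the protocol's own definition, and loss of response already shows in the ACR rows across the OLE.

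**Conclusion.** The point holds in limited form. Table RHCG.6.8 applies to an unfavourable event a rule written for favourable ones, and the direction is not defined. On the natural reading the flare rate is multiplied by one minus the share imputed. The adalimumab row of the OLE Period Population is the firm case, since Week 16 switchers have nothing for LOCF to carry: 20% becomes 14% if 6 of 20 switch. The ixekizumab effect comes only from discontinuation and missing data and is likely small.

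The switch counts, dropout rates and flare rates are all assumptions, and the 71% behind the 6 of 20 comes from one JIA subtype at Week 12. Flare is summarised descriptively without inference (SAP Section 6.1), and the primary Bayesian decision does not depend on it. The plan should be changed, but the study's conclusion is not at risk.

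**What to change.** In Table RHCG.6.8 and Appendix 2:
- Make the main flare summary the proportion among participants on the assigned drug with evaluable flare status, with the not-evaluable, discontinued and switched counts beside it.
- Score more than three missing components as not evaluable.
- In the OLE Period Population, censor flare at the switch.
- State whether component LOCF or NRI takes precedence after discontinuation.
- Keep one NRI line as supplementary, with its direction stated, because protocol Section 10.3.1.5.1 calls for an NRI summary of every categorical efficacy variable.
- Optionally add a sensitivity line, labelled as flare or treatment failure, that also counts stops for lack of efficacy and the obligatory Week 16 switches. It should not be labelled flare, because it departs from the protocol's definition.

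The cost is SAP wording and one or two descriptive lines per table; no new data are needed. The drawback is that evaluable-only rates select those who stay on drug, which is why the counts and the sensitivity line belong beside them.
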